Study Phases Screening Study Treatment Follow-Up	This is a three-arm cluster randomized experiment in which all 147 public healthcare facilities located in Kisumu county will be randomly assigned to one of three study arms: 1. The Community Score Card treatment arm, 2. The Citizen Report Card treatment arm, and 3. The control arm. Each study arm will contain approximately 48 facilities, which, on average, serve approximately 2,500 households each. Prior to randomization, we will ensure the three arms each contain similar numbers of each type of facility by first stratifying by facility type, a designation that includes three categories: 1. clinics and dispensaries (the smallest public facility type); 2. health centers; and 3. hospitals (sub-county or county hospitals). Individual-level data will be collected form women of reproductive age (18-29) in the catchment area of each facility.
	Pre-intervention/baseline data collection will be conducted in 2021, with a repeated cross-sectional endline survey conducted in 2022/23.
Efficacy Evaluations	Individual level questionnaires with women of reproductive age
	Facility level data on family planning quality of care
Safety Evaluations	Given our focus on improving quality of care among health care providers and the fact that we are not administering drugs or invasive measures, we anticipate a limited number of adverse events. Nevertheless, community monitoring of provider performance may increase stress for either community members or providers; therefore, facility staff and community members participating in any study component will be instructed to report any perceived adverse events related to any portion of this study to local project personnel, who will in turn inform [name] throughout the trial.
Statistical And Analytic Plan	Our approach to testing the working hypothesis will be to use a difference-in-difference (DiD) model to estimate differential change in contraceptive use over time in each of the two treatment areas versus the control area. Contraceptive use will be a binary variable (0=non-use; 1=use), attained by asking participants, "Are you (or your partner) currently doing something or using any method to delay or avoid getting pregnant?" We will define modern contraceptive methods to include female or male sterilization, intrauterine device, implant, injectable contraception, oral contraceptive pill, or male or female condom.

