3.3 Study Duration, Enrollment and Number of Subjects

Mystery clients and unannounced visitors: All 147 public-sector healthcare facilities in Kisumu County will be included in this study. Each facility will receive two unannounced visitors and three mystery client visits at baseline and then again at endline.

Provider interviews: Provider interviews will be conducted in all 147 public facilities in Kisumu County at baseline and endline. The total number of provider interviews conducted per facility will depend on the facility size but will average three per facility and will range from one to ten. The unannounced visitor will take a roster of providers who offer family planning services that are scheduled to work that day. If the facility has more than ten providers who provide family planning services scheduled to work that day, then ten providers will be randomly selected to participated. If the facility has less than ten providers scheduled to work that day, then all providers who offer family planning services will be interviewed.

Individual-Level Interviews: 18 women will be sampled from each of the 42 clusters in each of the three arms. Households will be selected at random and approached by trained enumerators who will discuss the study and survey with the household head and then approach eligible women to review the consent process. This cross-sectional survey will be conducted at both baseline and endline.

In-depth interviews: Thirty qualitative in-depth interviews will be conducted at endline with providers and community members to explore nuanced perspectives on formal feedback mechanisms and impact on provider job fulfillment. The UNC-based and local research teams will use convenience sampling to ensure that community members and providers who participated in the interventions are included. Once potential respondents have been identified, the local partner will invite potential respondents to participate in the interviews.

Focus Group Discussions: Four focus group discussions will be conducted at endline with two groups per intervention arm. These discussions will bring together key facilitators who were instrumental in the implementation of the two interventions. The UNC-based team will work with our local partner to identify key figures in the implementation process and invite them to join these discussions. Approximately 55 individuals will be recruited to participate in these focus group discussions.

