The interaction between POST and T1 or T2 gives the difference between the change in the value of Y in either treatment group versus the same change in the control group. Equation (1) also includes a vector, X, of demographic characteristics. For any covariates that are not balanced across the study arms we will control for them in the regression, using their baseline values [47]. These covariates could include age, religion, ethnicity (tribal group), marital status, literacy/education, parity, distance to public facility, and household wealth. This model can also be used to test whether there is a large difference between the treatments by testing the equality of β 3 and β 5.

Expected Outcomes. This aim is expected to provide critical knowledge of whether social accountability efforts can increase family planning use in LICs. Additionally, this aim will determine whether the two primary approaches to community engagement are largely different in their impact on women's contraceptive behavior. This work is crucial to global efforts to address facility-level barriers to contraceptive use.

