6.1 Sample Size and Power

For the *individual*-level surveys, we estimate a design effect of 1.56 for modern contraceptive prevalence due to our cluster-based sampling procedure, based on information provided in the 2014 Kenya Demographic and Health Survey (KDHS) Final Report, Appendix B, Table B2. We calculate our necessary sample size assuming 1.) 50% current modern contraceptive prevalence in Kisumu; 2.) 42 clusters in each study arm [clusters=facility catchment areas (All public facilities have a catchment area which is clearly defined, mutually exclusive, and exhaustive); we are allowing for potential closure of one facility per arm)]; 3.) an effect size of two standard deviations (which correlates to a change in the prevalence of modern contraceptive use of approximately 10 percentage points). With these parameters, we will need to survey 18 women in each of the 42 clusters in each of the three study arms, resulting in a total sample size of 2,268 women of reproductive age in the individual-level surveys. The 18 women sampled from each cluster will be selected at random. We will follow KDHS procedures in cases where there is more than one eligible woman in the household.

For the *facility*-level surveys we will measure family planning service quality and negative provider behaviors via interviews with one to ten providers, depending on total staff at each of the 147 facilities. This will result in approximately 385 provider interviews, with approximately 128 in each study arm. Unannounced visitors and mystery clients will also be deployed to secure less biased estimates of provider absenteeism, informal fee solicitation, and disrespectful/biased treatment of clients; mystery clients will also collect data on traditional measures of family planning service quality such as choice of methods and information on side effects. All 147 facilities in Kisumu will receive two unannounced visits and three mystery client visits.

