Post-treatment, we will repeat the individual-level survey, within a newly sampled cross-section of the population. We will also repeat all facility-level data collection in all 147 public facilities in the county. The changes in contraceptive use, quality of care, and community engagement resulting from the Community Score Card and the Citizen Report Card interventions will be evaluated via data collected in these pre- and post-intervention surveys. The sampling frame for both individual-level surveys will come from the Kenyan National Bureau of Statistics, which completed a new household-level census in all counties in Kenya in August 2019.

7 STUDY INTERVENTION (drug, device or other intervention details)

- Description

The Community Score Card Approach

In the Community Score Card approach, community members come together to document challenges they encounter when seeking services and develop a corresponding set of indicators that can be used to produce a validated facility score. The score is shared with the community and a collaborative process between key community members and facility staff takes place to develop feasible solutions

and a strategic action plan.

Step 1: Preparation (3 months). During this phase, the PI will consult with the Kisumu County Health Director to confirm the geographic coverage of the community score card intervention (the catchment area of the 43 public healthcare facilities in this arm). Training manuals and facilitation guides will be developed. Experienced facilitators will be identified and trained in the community score-card approach. The communities and facility staff will be engaged and sensitized to the community score card via a meeting that discusses the community score card purpose and approach; a date, location, and general process for conducting the community score cards will be selected/designed.

Step 2: Conducting the community score card with target communities (1 month). During this phase, all communities associated with the targeted facilities will assess the primary barriers to quality family planning service delivery and develop corresponding indicators, assisted by an experienced facilitator. The communities will then each complete the score card and generate ideas for quality improvement.

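### Section 6.1 calls a 10-point change two standard deviations when at 50% prevalence it is 0.2 SD, and it omits the alpha, power, contrast and between-wave correlation needed to see what 18 women per cluster was sized for

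*Combined protocol and SAP*

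**What the plan says.** Section 6.1 takes a design effect of 1.56 from a national survey report, 50% current modern contraceptive prevalence, 42 clusters per arm and "an effect size of two standard deviations (which correlates to a change in the prevalence of modern contraceptive use of approximately 10 percentage points". It then concludes: "With these parameters, we will need to survey 18 women in each of the 42 clusters in each of the three study arms", 2,268 women in all. Section 3.3 repeats this ("18 women will be sampled from each of the 42 clusters in each of the three arms") and says that the survey takes place at baseline and at endline. At endline, "we will repeat the individual-level survey, within a newly sampled cross-section of the population".

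The primary analysis in Section 6 is a DiD regression on the stacked waves: "The interaction between POST and T1 or T2 gives the difference between the change in the value of Y in either treatment group" and the same change in control. On covariates, "Equation (1) also includes a vector, X, of demographic characteristics".

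The number of clusters varies across the document. The synopsis says "Each study arm will contain approximately 48 facilities", Sections 3.1, 3.2 and 7 say 43, and Sections 3.3 and 6.1 use 42.

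**The concern.** The effect size is the main input to a sample-size calculation, and here its two expressions differ by a factor of ten. The sentence also presents 18 as following from the listed parameters, but alpha, sidedness, power, any allowance for two treatment comparisons and the between-wave cluster correlation are all absent. So is a statement of whether the calculation is for one wave or for the DiD interaction.

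That last gap matters because a DiD on fresh cross-sections carries the sampling error of both waves, while a single-wave comparison carries only one. If the calculation was for a single wave, the planned analysis has less power than was intended. If it was for the DiD, it needed an assumption about cluster stability that is not written down. A reader cannot tell which.

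**Working it through.** **Inputs from the documents.** Prevalence 0.50; effect 0.10; design effect (DEFF) 1.56; m = 18 women per cluster per wave; k = 42 clusters per arm (Sections 3.3 and 6.1) or 48 (synopsis).

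**Assumptions not in the documents.** Two-sided 0.05; DEFF applies at 18 women per cluster; no covariate gain; same clusters in both waves; inference that respects clustering; normal approximation; cluster autocorrelation (CAC) anywhere from 0 to 1.

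**1. The plan's total.** 18 × 42 = 756 per arm and 756 × 3 = 2,268. The product is correct.

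**2. The effect size.** SD = √(0.5 × 0.5) = 0.5, and 0.10 / 0.5 = 0.2 SD. Two SD would be 1.00, or 100 points. Sizing for two SD needs 2 × (1.96 + 0.84)² / 2² = 3.9, about 4 women per arm before clustering, so the 10-point figure must have driven the calculation. The SD of an 18-woman cluster mean does not rescue the phrase: 0.5 × √(1.56/18) = 0.147, and 0.10 / 0.147 = 0.68.

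**3. Which designs give 18?** For one wave, n per arm = (z_α + z_β)² × 2 × 0.25 × 1.56 / 0.10².
- Single wave, two-sided 0.05, 80% power: about 613 per arm, 14.6 per cluster, so 15.
- Single wave, two-sided 0.05, 90% power: about 821 per arm, 19.5 per cluster, so 20.
- Endline comparison, two-sided 0.025 (two treatment comparisons), 80% power: about 743 per arm, 17.7 per cluster, so 18 and a total of 2,268.
- DiD with fully stable clusters (CAC 1), two-sided 0.05, 80% power: n = (1.96 + 0.84)² × S × (1 − ICC) / 0.10², where the intracluster correlation (ICC) is 0.56/17 = 0.033 and S sums p(1 − p) over the four arm-by-wave cells. S = 0.99 (treated endline at 60%) gives 752; S = 1.00 (50% throughout) gives 759. Planned: 756.

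Two different designs therefore land on 18, and the text does not identify either.

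**4. Power of the planned data for 10 points.** Let V = 2 × 0.25 × 1.56 / (18k), the variance of a one-wave difference between two arms, and r = 18 × ICC × CAC / 1.56, the between-wave correlation of cluster means.
- SE(DiD) = √[V × 2(1 − r)]
- SE(baseline-adjusted) = √[V × (1 − r²)]
- Power = Φ(0.10/SE − 1.96)

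| CAC | 0 | 0.5 | 0.8 | 1 |
|---|---|---|---|---|
| r | 0 | 0.190 | 0.304 | 0.380 |
| SE of DiD, points (k = 42) | 4.54 | 4.09 | 3.79 | 3.58 |
| DiD power, k = 42 | 59.5% | 68.7% | 75.1% | 79.8% |
| DiD effect detectable at 80% power, points (k = 42) | 12.7 | 11.5 | 10.6 | 10.0 |
| SE of adjusted estimate, points (k = 42) | 3.21 | 3.15 | 3.06 | 2.97 |
| Adjusted power, k = 42 | 87.6% | 88.7% | 90.5% | 92.0% |
| DiD power, k = 48 | 65.3% | 74.4% | 80.5% | 84.8% |
| Adjusted power, k = 48 | 91.4% | 92.4% | 93.7% | 94.9% |

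The ranking does not depend on the assumed CAC: 2(1 − r) − (1 − r²) = (1 − r)² ≥ 0, so adjustment is never less precise, apart from one degree of freedom. Simulated cluster-level t tests (4,000 trials per scenario) agreed: at k = 42, DiD power was 59.4 / 68.4 / 75.9 / 80.0% and adjusted power 88.3 / 88.0 / 90.4 / 91.6%.

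**5. Sensitivity.** The cluster size behind 1.56 is not given. If it came from clusters of 10 to 30 women (ICC 0.062 to 0.019), then at k = 42 and across all CAC values DiD power spans 48–81% and adjusted power 77–94%. Covariates work the other way: removing 11% of the residual variance at CAC 0.8, or 24% at CAC 0.5, brings the DiD to 80%. The plan gives no R².

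**The case against.** The strongest reply is that only a label is wrong. The planning effect is given in plain units, 10 percentage points, and the total is multiplied correctly. The phrase may even be a slip for two standard errors: with independent waves the DiD standard error is 4.54 points, so two of them make 9.1. That cannot be shown, but it is a reason to let the sponsor drop the SD phrase instead of insisting on one reading of it.

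A reader might infer from the missing inputs that 18 is wrong. The documents do not support that, since two ordinary designs give about 18. A reader might also infer that the trial is underpowered. That is not supported either: no power target is stated, alpha, ICC and autocorrelation are not in the plan, and with 48 clusters the DiD reaches 80% at an autocorrelation of about 0.78 or above. The covariates in equation (1) could help further. Nor is the DiD biased, because it is valid under randomisation.

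One can also object that baseline adjustment needs the same clusters in both waves, and that Section 2.1 calls the two surveys independent. Section 3.3 largely answers this, because it samples 18 women from each of the 42 clusters and repeats that survey at baseline and endline. The condition should still be confirmed. What stands of the objection is that changing the estimator is an improvement on offer, not the correction of an error.

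**Conclusion.** Two things are certain from the document alone. The effect-size phrase is wrong by a factor of ten for the SD of the outcome, and the inputs needed to trace 18 women per cluster are absent.

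The power figures are conditional. Under the assumptions listed in the working, the DiD has about 60–80% power for 10 points with 42 clusters per arm and 65–85% with 48, against 88–92% and 91–95% for the baseline-adjusted estimate. A different ICC widens these ranges. As an illustration, with 42 clusters and autocorrelation of 0.5 to 0.8, the DiD would miss a true 10-point effect 25–31% of the time and the adjusted analysis 10–11%. Power below a conventional 80% is possible, but it is not established. The point should be fixed; it does not call the validity of the trial into question.

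**What to change.** 1. In Section 6.1, replace the SD phrase with: 10 percentage points (0.2 SD of the binary outcome at 50% prevalence). Alternatively, drop the SD phrase and keep the 10 points. This costs one phrase.
2. State alpha, sidedness, the contrast and the assumed ICC and between-wave correlation, and give power or detectable effect for the DiD interaction as a range. With two-sided 0.05, 42 clusters and autocorrelation 0.5 to 0.8, for example, the effect detectable at 80% power is 11.5 to 10.6 points. This adds no women. Its downside is a less favourable stated power if the DiD stays primary.
3. If endline outcomes have not been seen and both waves survey the same clusters, estimate the effect from endline use regressed on T1, T2, facility baseline prevalence and facility type, with cluster-level inference, and keep the DiD as a sensitivity analysis. Otherwise keep the DiD primary and report the adjusted analysis as supportive. This uses data that the trial already plans to collect. Its cost is a documented change of estimator, to be explained to readers who expect a DiD, and its benefit is precision. Items 1 and 2 stand even if item 3 is declined.

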3.1 Study Design

This is a three-arm cluster randomized experiment in which all 147 public healthcare facilities located in Kisumu county will be randomly assigned to one of three study arms: 1. The Community Score Card treatment arm, 2. The Citizen Report Card treatment arm, and 3. The control arm. Each study arm will contain approximately 43 facilities, which, on average, serve approximately 2,500 households each. Prior to randomization, we will ensure the three arms each contain similar numbers of each type of facility by first stratifying by facility type, a designation that includes three categories: 1. clinics and dispensaries (the smallest public facility type); 2. health centers; and 3. hospitals (sub-county or county hospitals).

Before and after implementing the two treatments, individual- and facility-level pre- and postintervention surveys will be conducted. The *individual*-level surveys will be conducted within a representative sample of women of reproductive age, stratified by study arm and cluster, and will be used to establish the primary outcome, modern contraceptive use, in all three study arms, pre- and post-treatment. The individual-level surveys will also measure multiple linking constructs such as community empowerment and quality of care. The *facility*-level surveys will be conducted in a census of all public-sector facilities located in Kisumu county and will be used to measure quality of family planning service delivery and negative provider behaviors.

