3.2 Allocation to Treatment Groups

This is a three-arm cluster randomized experiment in which all 147 public healthcare facilities located in Kisumu county will be randomly assigned to one of three study arms: 1. The Community Score Card treatment arm, 2. The Citizen Report Card treatment arm, and 3. The control arm. Each study arm will contain approximately 43 facilities, which, on average, serve approximately 2,500 households each. Prior to randomization, we will ensure the three arms each contain similar numbers of each type of facility by first stratifying by facility type, a designation that includes three categories: 1. clinics and dispensaries (the smallest public facility type); 2. health centers; and 3. hospitals (sub-county or county hospitals).

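### All 147 facilities are randomised (49 per arm), but the women's survey is sized on 42 clusters per arm and other sections give 43, so the cluster count and the target of 2,268 do not match the randomised set

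*Combined protocol and SAP*

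**What the plan says.** Section 3.1 states that "all 147 public healthcare facilities located in Kisumu county will be randomly assigned to one of three study arms". The synopsis (Study Phases) repeats the 147, adds that "Each study arm will contain approximately 48 facilities", and places the women's survey "in the catchment area of each facility".

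Straight after the 147, section 3.1 says: "Each study arm will contain approximately 43 facilities, which, on average, serve approximately 2,500 households each". Section 3.2 gives the same pair of figures. Section 7 (Community Score Card, Step 1) refers to "the catchment area of the 43 public healthcare facilities in this arm", here without any qualifier.

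For the women's survey, section 3.3 says that "18 women will be sampled from each of the 42 clusters in each of the three arms", and section 6.1 concludes: "With these parameters, we will need to survey 18 women in each of the 42 clusters in each of the three study arms", which it totals to 2,268. Section 6.1 equates clusters with facility catchment areas, describes those areas as exhaustive, and explains the 42 as allowing for one closure in each arm. The same section plans provider interviews, unannounced visits and mystery-client visits at all 147 facilities, with about 385 provider interviews in total. Section 3.3 gives an average of three provider interviews per facility.

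**The concern.** If every facility is randomised and every facility has one catchment, 147 facilities means 147 clusters. The sample-size paragraph works with 126. The cluster count feeds the only sample-size calculation for the primary outcome, and it fixes how many women are interviewed in each catchment.

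As the text stands, a field team cannot tell whether the target per wave is 2,268, 2,592 (18 × 48 × 3) or 2,646 (18 × 49 × 3), nor whether any catchments are to be left out. If some were left out, there is no rule for choosing them. Section 7 also leaves unclear how many catchments receive the Community Score Card.

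**Working it through.** **Inputs.** 147 facilities (synopsis, 3.1, 3.2, 3.3, 6.1); about 48 per arm (synopsis); about 43 per arm (3.1, 3.2) and 43 (section 7); 42 clusters per arm, 18 women per cluster, design effect 1.56 and one closure per arm (6.1); about 385 provider interviews (6.1) at an average of three per facility (3.3).

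**The plan's own figure.** 18 × 42 × 3 = 2,268, or 18 × 42 = 756 women per arm. The product is correct; the issue is the 42.

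**The counts side by side.**

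| Per arm | × 3 | Relation to the other counts |
|---|---|---|
| 49 | 147 | equal split of the randomised set |
| about 48 | 144 | within one of 49, or 49 less one closure |
| about 43 | 129 | six below 49; not explained |
| 42 | 126 | 43 less one closure; seven below 49 |

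The figures form two families: 147/49/48 and 129/43/42. Each is coherent within itself. The conflict is between them: 147 − 126 = 21 catchments, of which the closure allowance accounts for 3.

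**Provider interviews as a check.** 385/129 = 2.98 per facility, which matches the stated average of three (3 × 129 = 387). 385/147 = 2.62, while 3 × 147 = 441. The 385 therefore also fits a count near 129, although section 6.1 ties it to 147.

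**Women per catchment if 147 is current.** Section 6.1 takes 1.56 as a fixed factor from an outside survey and does not build it up from cluster size. Used that way, the requirement of 756 women per arm does not depend on the number of clusters; only the number per cluster does.

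- 49 clusters: 756/49 = 15.43, rounded up to 16.
- 48 clusters: 756/48 = 15.75, rounded up to 16.
- 16 × 49 = 784 and 16 × 48 = 768 per arm, both at least 756.
- 15 × 49 = 735 and 15 × 48 = 720 per arm, both short of 756.
- Totals per wave at 16: 16 × 147 = 2,352 (+84), or 16 × 144 = 2,304 (+36) after three closures. At 18: 18 × 147 = 2,646 (+378).

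**Effect on precision.** Effective size per arm per wave is 756/1.56 = 485 as written. At 16 per catchment it is 784/1.56 = 503 with 49 clusters and 768/1.56 = 492 with 48. If 1.56 is instead assumed to apply at 18 women per cluster, the implied intracluster correlation is 0.56/17 = 0.033. The design effect at 16 is then 1 + 15 × 0.56/17 = 1.494, giving 784/1.494 = 525 and 768/1.494 = 514. Precision is not reduced on either basis.

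**What cannot be checked.** Section 6.1 states neither alpha nor power, so the step from a 10-point effect to 18 women can be matched only by assumption. For 50% against 60% at a single time point with 42 clusters, two-sided 5% gives 15 per cluster at 80% power and 20 at 90%. Two-sided 2.5% at 80% power gives 470 × 1.56 = 733.2 per arm, and 733.2/42 = 17.46, rounded up to 18. On that last assumption, 48 clusters would need 733.2/48 = 15.28, again 16.

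**The case against.** Much can be said in the plan's defence, and several stronger readings should be set aside.

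- A reader might list 48 as a further contradiction. It is not one: the synopsis says approximately, and 48 is either a rounding of 49 or 49 less one closure.
- A reader might infer that 21 of 147 randomised catchments (14.3%) will have no primary-outcome data. That follows only if 42 is taken literally. The synopsis places the survey in every facility's catchment, section 6.1 calls catchments exhaustive, and nothing describes subsampling. The likelier reading is that 42 is a planning figure that was not updated.
- A reader might instead conclude that 147 is the error. It appears throughout the document, whereas 129 is printed nowhere.
- A reader might infer that the trial is underpowered because of the count. The documents do not show this. More clusters with about the same number of interviews leave precision about the same or slightly better, and any power figure needs an alpha and a between-wave correlation that the plan does not give.
- A reader might expect the overall 5,500 to be wrong as well. One reconstruction of the figures as written gives 2 × 2,268 + 2 × 385 + 30 + 55 + 40 = 5,431, close enough to 5,500 that no error is shown.

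These points limit the consequence. They do not remove the conflict between 147 and 43/42, which neither rounding nor the closure allowance can bridge.

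**Conclusion.** The inconsistency stands. The randomised set gives 49 clusters per arm, or 48 after the plan's own closure allowance, while the primary-outcome survey is sized on 42 and three sections give 43. The gap is 7 clusters per arm, 21 in total, 18 of them beyond the allowance. The consequence is ambiguity about the cluster count and the target number of women, in a paragraph that needs redoing; it is neither a demonstrated loss of power nor a bias.

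This assumes equal allocation and that 147 is the current count. That 43, 42 and 385 survive from a count near 129 is an inference from their mutual fit. The figure of 16 women per catchment assumes that 756 per arm is the requirement and that 1.56 is applied as a fixed factor.

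**What to change.** State one facility count and bring sections 3.1, 3.2, 3.3, 6.1 and 7 into line with it.

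If 147 is current, say that women are surveyed in every randomised catchment, and redo the sample-size paragraph with 49 clusters per arm (48 after the closure allowance), giving the alpha and power used. Under the fixed 1.56, 16 women per catchment is the smallest whole number that preserves the planned size per arm; the redone calculation should confirm it or show that 18 each is needed.

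If only 42 catchments per arm can be surveyed, say so and pre-specify a random draw within arm and facility type. Restate the provider-interview total on the same facility count; it is 441 if the average of three is kept.

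The cost is a text correction, one recalculation and, at 16 per catchment, up to 84 more women's interviews and up to 21 more catchments to visit in each wave.
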